## **10.5.2 Other secondary efficacy objectives**

### **10.5.2.1 Overall response rate**

Overall response rate (ORR) is defined as the proportion of patients with best overall response (BOR) of complete response (CR) or partial response (PR) according to RECIST 1.1.

ORR will be calculated based on the FAS according to the ITT principle; however patients with only non-measurable disease at baseline will be included in the numerator if they achieve a complete response. ORR will be presented by treatment group along with approximate 95% confidence intervals. The Cochran-Mantel Haenszel chi-square test (stratified by baseline stratification factor) will be used to compare the two treatment groups with respect to the ORR at one-sided 2.5% level of significance. As a supportive analysis, ORR as assessed by the blinded independent central review will be calculated by treatment group and presented along with the approximate 95% confidence intervals. As a sensitivity analysis, ORR for patients with measurable disease at baseline will be calculated and presented by treatment group together with approximate 95% confidence intervals.

### **10.5.2.2 Clinical benefit rate**

Clinical Benefit is defined as CR, PR or SD for 24 weeks or longer. CR, PR and SD are defined according to RECIST 1.1. CBR will be calculated based on the FAS; however patients with only non-measurable disease at baseline will be included in the numerator if they achieve a complete response. CBR will be summarized for the two treatment groups using descriptive statistics. The Cochran-Mantel Haenszel chi-square test (stratified by baseline stratification factor) at 2.5% one-sided level of significance, will be used to compare the two treatment groups with respect to the CBR. As a supportive analysis, CBR as assessed by the blinded independent central review will be summarized for the two treatment groups using descriptive statistics.

### **10.5.2.3 Time to response**

Time to response is the time from the date of randomization to the first documented response (CR or PR, which must be confirmed subsequently) according to RECIST 1.1. All patients will be included in time to response calculations. Patients who do not achieve a confirmed response will be censored at the maximum follow-up time (i.e. first patient first visit to last patient last visit used for the analysis) for patients who had a PFS event (i.e. either progressed or died due to any cause) or at the date of last adequate tumor assessment. Time to response data will be listed and summarized by treatment group. The distribution of time to response may be summarized through Kaplan-Meier method if sufficient number of events are observed.

### **10.5.2.4 Duration of response**

Duration of Overall Response (DoR) applies only to patients whose best overall response is CR or PR according to RECIST 1.1. The start date is the date of first documented response (CR or PR) and the end date is the date defined as first documented progression or death due to underlying cancer. In other words, the start date should be determined using the time that the response was first determined and not using the time the response was confirmed. If a patient had not had an event, duration will be censored at the date of last adequate tumor assessment. DoR will be listed and summarized by treatment arm.

### **10.5.2.5 ECOG performance status**

ECOG PS scale as described in [Section 7.2.2.4](#) will be used to assess physical health of patients. An analysis of time to definitive deterioration of the ECOG PS by one category of the score from baseline will be performed. Deterioration is considered definitive if no improvements in ECOG PS status is observed at a subsequent time of measurement during the treatment period following the time point where the deterioration is observed.

Patients receiving any further therapy prior to definitive worsening will be censored at their date of last assessment prior to start of therapy. Patients that have not worsened at the data cut-off point will be censored at the date of last assessment prior to start of therapy. Kaplan-Meier method will be used to estimate the distribution of time to definitive worsening and median time to definitive worsening will be presented along with a 95% confidence interval. A stratified log-rank test at one-sided 2.5% level of significance will be used to compare the distribution of time to definitive worsening between the 2 treatment arms.

### **10.5.3 Safety objectives**

#### **10.5.3.1 Analysis set and grouping for the analyses**

For all safety analyses, the safety set will be used. All listings and tables will be presented by treatment group. In addition, for the final study report, safety data for patients who crossed over to the LEE011 combination arm after the study had met its primary and secondary endpoint of OS, will be summarized using the crossover analysis set. The analyses will comprise a subset of those described below for the safety set and the details will be specified in the SAP.

The overall observation period will be divided into three mutually exclusive segments:

1. pre-treatment period: from day of patient's informed consent to the day before first dose of study medication
2. on-treatment period: from day of first dose of study medication to 30 days after last dose of study medication
3. post-treatment period: starting at day 31 after last dose of study medication.

#### **10.5.3.2 Adverse events (AEs)**

Summary tables for adverse events (AEs) have to include only AEs that started or worsened during the on-treatment period, the treatment-emergent AEs. However, all safety data (including those from the pre and post-treatment periods) will be listed and those collected during the pre-treatment and post-treatment period are to be flagged.

The incidence of treatment-emergent adverse events (new or worsening from baseline) will be summarized by system organ class and or preferred term, severity (based on CTCAE grades), type of adverse event, relation to study treatment by treatment group.

Deaths reportable as SAEs and non-fatal serious adverse events will be listed by patient and tabulated by type of adverse event and treatment group.

Specific safety event categories (SEC) will be considered. Such categories consist of one or more well-defined safety events which are similar in nature and for which there is a specific clinical interest in connection with the study treatment(s). SEC will be defined at project level

and may be regularly updated. The grouping of AEs in SEC according to project standards will be specified in the project level master statistical analysis and/or the study statistical analysis plan.

For each specified SEC, number and percentage of patients with at least one event part of the SEC will be reported by treatment group

### **10.5.3.3 Laboratory abnormalities**

For laboratory tests covered by the Common Terminology Criteria for Adverse Events (CTCAE) version 4.03, the study's biostatistical and reporting team will grade laboratory data accordingly. For laboratory tests covered by CTCAE, a Grade 0 will be assigned for all non-missing values not graded as 1 or higher. Grade 5 will not be used.

In some cases (e.g., white blood cell differentials), the lower limits of normal ranges used in CTCAE definition have to be replaced by a clinical meaningful limit expressed in absolute counts.

For laboratory tests where grades are not defined by CTCAE, results will be graded by the low/normal/high classifications based on laboratory normal ranges.

The following by-treatment summaries will be generated separately for hematology, biochemistry and urinary laboratory tests:

- frequency table for newly occurring on-treatment grades 3 or 4
- shift tables using CTCAE grades to compare baseline to the worst on-treatment value
- for laboratory tests where CTCAE grades are not defined, shift tables using the low/normal/high/(low and high)
- classification to compare baseline to the worst on-treatment value.
- listing of all laboratory data with values flagged to show the corresponding CTCAE grades and the classifications relative to the laboratory normal ranges.

In addition to the above mentioned tables and listings, [REDACTED] might be specified in the analysis plan.

[figure not shown]
### **10.5.3.4 Other safety data**

#### **10.5.3.4.1 ECG**

- shift table from baseline to worst on-treatment result for overall assessments
- listing of ECG evaluations for all patients with at least one abnormality.

#### **10.5.3.4.2 Vital signs**

- shift table from baseline to worst on-treatment result
- table with descriptive statistics at baseline, one or several post-baseline time points and change from baseline to this/these post-baseline time points.

### **10.5.3.5 Tolerability**

Tolerability will be studied in terms of dose reductions and drug interruptions due to AE. Reasons for dose reductions and interruptions will be listed and summarized by treatment.

### **10.5.4 Pharmacokinetics**

PK concentrations of ribociclib (and any relevant metabolites such as LEQ803) will be summarized by time point using descriptive statistics by treatment only for fulvestrant + ribociclib arm. All PK concentration data will be listed as appropriate.

#### **10.5.4.1 Data handling principles**

Plasma samples will be assayed for ribociclib concentrations by Novartis or Novartis designated laboratory using validated LC-MS/MS methods with a LLOQ of approximately 1.00 ng/mL for ribociclib.

All concentrations below the LLOQ will be displayed in listings as zero with a flag and handled as zero in any calculations of summary statistics, but handled as missing for the calculation of the geometric means and their CV. Any missing PK parameter data will not to be imputed.

### **10.5.5 Patient-reported outcomes**

The EORTC QLQ-C30 questionnaire and the EuroQol EQ-5D-5L will be used to collect patient's QoL data. The BPI-SF will be used to assess patient's subjective assessment of cancer-related pain. The global health status/QoL scale score of the QLQ-C30 is identified as the primary patient-reported outcome variable of interest. Physical functioning, emotional functioning and social functioning scale scores of the QLQ-C30, the health status index score and overall health status of the EQ-5D-5L, and worst pain item (based on question 3), pain severity index, and pain interference indices of the BPI-SF are identified as secondary patient-reported QoL variables of interest.

Scoring of PRO data and methods for handling of missing items or missing assessments will be handled according to the scoring manual and user guide for each respective patient questionnaire (Fayers 2001; Oemar and Janssen 2013; Cleeland 2009). No imputation procedures will be applied for missing items or missing assessments. Five health states from the EQ-5D-5L will be converted to index values during the data analysis stage and will be further defined in the analysis plan. In addition, the visual analog scale (ranging from 0 to 100) will be evaluated for patient's rating of their overall health status.

The number of patients completing the each questionnaire and the number of missing or incomplete assessments will be summarized by treatment group for each scheduled assessment time points for each cohort. No formal statistical tests will be performed of PRO data and hence no multiplicity adjustment will be applied. The FAS will be used for analyzing PRO data.

Descriptive statistics will be used to summarize the scored scales of the QLQ-C30; health states, overall health status, and index values of the EQ-5D-5L, and the worst pain item (question 3), pain severity index, and pain interference indices of the BPI-SF at each scheduled assessment time point for each cohort. Additionally, change from baseline in the domain scores, health states, overall health status, and index values at the time of each assessment will be summarized.

[figure not shown]
[figure not shown]
Shift tables will be produced to describe worsening of pain from baseline based on the worst pain item from the BPI-SF. Patients with an evaluable baseline score and at least one evaluable post baseline score during the treatment period will be included in the change from baseline analyses.

[figure not shown]
[figure not shown]
In addition, a repeated measurement analysis model may be used to compare the two treatment groups with respect to changes in the domain scores (global health status/QoL scale score, physical functioning, emotional functioning and social functioning scale scores of the QLQ-C30 index score and overall health status of the EQ-5D-5L, longitudinally over time. [REDACTED]

[figure not shown]
Time to definitive 10% deterioration in the global health status/QoL, physical functioning, emotional functioning, social functioning will be assessed. The time to definitive 10% deterioration is defined as the time from the date of randomization to the date of event, which is defined as at least 10% relative to baseline worsening of the corresponding scale score or death due to any cause. If a patient has not had an event, time to deterioration will be censored at the date of the last adequate QoL evaluation. The distribution will be presented descriptively using Kaplan-Meier curves. Summary statistics from Kaplan-Meier distributions will be determined, including the median time to definitive 10% deterioration along with two-sided 95% confidence interval. Additionally, time to definitive deterioration with different cutoff definitions (e.g. 5%, 15%) may be specified in the RAP as deemed appropriate. A stratified Cox regression will be used to estimate the hazard ratio (HR), along with two-sided 95% confidence interval.

[REDACTED]

[REDACTED]

## **10.7 Interim analysis**

### **10.7.1 Progression free survival**

No PFS interim analysis is planned in this study.

### **10.7.2 Overall survival (OS)**

OS will be compared between the two treatment groups, provided the primary endpoint PFS is statistically significant favoring the test treatment arm (ribociclib + fulvestrant). A gatekeeping testing procedure will be adopted in this study and the OS analyses will be performed only if the primary efficacy endpoint PFS is statistically significant. A maximum of 3 analyses is planned for OS; at the time of the final analysis for PFS (provided PFS is significant), at which point approximately 161 deaths are expected, after approximately 263 events have been

documented), and a final analysis for OS when approximately 351 deaths are expected (expected 56 months from date of first patient to be randomized).

An  $\alpha$ -spending function according to Lan-DeMets (O'Brien-Fleming) independent of the one used for the primary efficacy analysis, (as implemented in East 6.3) along with the testing strategy outlined below will be used to maintain the overall type I error probability (Lan and DeMets 1983). This guarantees the protection of the 2.5% overall level of significance across the two hypotheses and the repeated testing of the OS hypotheses in the interim and the final analysis (Glimm 2010). The trial allows for the stopping of the study for a superior OS result, provided the primary endpoint PFS has already been shown to be statistically significant favoring the test treatment arm (ribociclib +fulvestrant). Further, the exact nominal p-values that will need to be observed to declare statistical significance at the time of these analyses for OS will depend on the number of OS events that have been observed at the time of these analyses and the  $\alpha$  for OS already spent at the time of earlier analyses.

The projected timing of interim analysis is summarized in Table 10-1.

**Table 10-1 Estimated timelines for interim and final analyses**

Months after randomization of the first patient	PFS events	Power (%) against a hazard ratio of 0.67	OS events	Cumulative Conditional Power (%) against hazard ratio of 0.71
26	364 (100%)	90	161(46%)	14
39	--	--	263(75%)	60
56	--	--	351(100%)	85

Statistical significance of OS will only be declared if significance for primary PFS analysis has been declared.

At the time of final PFS analyses, both PFS and interim OS analysis will be performed by the Sponsor's clinical team. Investigators and patients will remain blinded to study treatment and all patients will continue to be followed for OS until the final OS analysis (or earlier if OS reaches statistical significance at any of the interim analyses).

Since the study has met its primary endpoint (PFS) and the secondary endpoint (OS), any analysis and update after protocol amendment 4 will be descriptive.

## 10.8 Sample size calculation

The median time to progression (TTP) for fulvestrant in first line post-menopausal advanced breast cancer patients is estimated to be between 8 month (Howell 2004) and 23 months in FIRST trial (Robertson et al 2012). For sample size calculation, the median PFS for 1st line patients is assumed to be 18 month. The median PFS for fulvestrant in relapsed advanced breast cancer is estimated to be between 4.8 months (SoFEA trial, Johnston et al 2013) and 6.5 months (CONFIRM trial, Di Leo et al 2010). Since the study population is closer to the population in CONFIRM trial, for sample size calculation, the mPFS for fulvestrant in second line is assumed to be 6.5 months. It is assumed that 40% and 60% of the patients will be from first line and second line respectively. The median PFS in the control arm (fulvestrant + placebo) is estimated via simulation to be around 9 months. It is hypothesized that the addition of ribociclib will result in a clinically meaningful 33% reduction in the hazard rate of PFS, corresponding to an increase

in median PFS to 13.4 months. A maximum of 364 PFS events will be required to detect a hazard ratio of 0.67 with 95% power using the log-rank test at one-sided cumulative 2.5% level of significance (EAST 6.3). The increase in power from 90% to 95% while targeting the same hazard ratio and the number of events as in the original protocol is primary due to the elimination of the futility interim analysis. Assuming that enrollment will continue for approximately 19 months at a uniform rate and 10% dropout rate by the time of PFS final analysis, a total of 660 patients should be randomized to the two treatment groups in 2:1 ratio to observe 364 events at approximately 7 months following the randomization of the last patient, i.e., 26 months from the randomization date of the first patient in this study. The sample size calculation was conducted with software package East 6.3. The sample size calculations are based on the estimates from data available from prior studies. A mid-study sample size re-assessment based on blinded pooled data may be performed prior to any efficacy analysis if data from the study indicate substantial deviation from the study assumptions. A Monte-Carlo simulation based on 10,000 samples was carried out to characterize the probability of the study outcomes under various assumptions of the true hazard ratios (Table 10-2). If the alternative hypothesis is true, that is, the true hazard ratio is 0.67, then there is 96% probability the primary analysis will be statistically significant.

[figure not shown]
**Table 10-2 Probability of Study Outcomes under various true Hazard Ratios**

True Hazard Ratio	% statistical significance*
0.5	100
0.6	99.7
0.67	96
0.7	91
0.8	53
0.9	16
A total of 660 patients will be enrolled with exponential dropout hazard rate 0.0105 (about 10% drop out rate) *: Based on 10,000 simulations using EAST 6.3	

The primary objective of the study is to compare investigator assessed PFS between arms in the overall population (both 1st line and 2nd line patients). If the primary analysis is statistically significant, treatment effect will be evaluated in 1st and 2nd line patients separately. Based on the estimated median PFS and proportion of patients in 1st line and 2nd line respectively, it is expected that the accumulation of events in 1st line will be slower than 2nd line patients. To ensure enough information coming from 1st line patients, the final analysis will be done after approximately 125 events in the first line patients or approximately 364 events in both arms whichever comes later.

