2.2 Data included in the analysis

The primary PFS analysis will be carried out after approximately 364 events have been documented based on local investigator assessment. Up to 3 analyses for OS may be performed as described in section 3.8. For each of the analysis time points, statistical analyses will be performed using all data collected in the database up to the data cutoff date. Any data

collected beyond the cutoff date will not be included in the analysis and will not be used for any derivations.

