3.14.2 Overall Survival

Overall survival will be compared between the two treatment groups, provided the primary endpoint PFS is statistically significant favoring the test treatment arm (fulvestrant + ribociclib). A hierarchical testing procedure will be adopted in this study and the treatment effect on OS will be tested only if the primary efficacy endpoint PFS is statistically significant. A maximum of 3 analyses are planned for OS: at the time of analysis for PFS (provided PFS is significant), at which point a total of 161 deaths are expected, after 263 events have been documented, and a final analysis for OS when 361 deaths are expected (expected 56 months from date of first patient to be randomized).

An α -spending function according to Lan-DeMets (O'Brien-Fleming), (as implemented in East 6.3) along with the testing strategy outlined below will be used to maintain the overall type I error probability (Lan and DeMets 1983). This guarantees the protection of the 2.5% overall level of significance across the two hypotheses and the repeated testing of the OS hypotheses in the interim and the final analysis (Glimm 2010). The trial allows for the stopping of the study for a superior OS result, provided the primary endpoint PFS has already been shown to be statistically significant favoring the test treatment arm (fulvestrant + ribociclib). Further, the exact nominal p-values that will need to be observed to declare statistical significance at the time of these analyses for OS will depend on the number of OS events that have been observed at the time of these analyses and the α for OS already spent at the time of earlier analyses.

The operating characteristics for OS are shown in Table 3-9 considering the hierarchical testing strategy of PFS and OS. The probabilities shown in Table 3-9 are conditional on PFS being statistically significant.

Statistical properties of the group sequential design are summarized in Table 3-9.

[figure not shown]
Table 3-9 Projected timelines for interim and final analyses

[figure not shown]
Months after randomization of the first patient	PFS events	Cumulative Power (%) against a hazard ratio of 0.67	OS events	Cumulative Conditional Power (%) against hazard ratio of 0.71
26	364 (100%)	95	161(46%)	14
39	--	--	263(75%)	60
56	--	--	351(100%)	85

Statistical significance of OS will only be declared if significance for primary PFS analysis has been declared.

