The primary objective of the study is to compare investigator assessed PFS between arms in the overall population (both 1st line and 2nd line patients). If the primary analysis is statistically significant, treatment effect will be evaluated in 1st and 2nd line patients (i.e. previous endocrine therapy stratification factor A and B as defined in section 1.1) separately. Based on the estimated median PFS and proportion of patients in 1st line and 2nd line respectively, it is expected that the accumulation of events in 1st line will be slower than 2nd line patients. To ensure enough information coming from 1st line patients, the final analysis will be done after approximately 125 events in the first line patients or approximately 364 events in both arms whichever comes later.

Audit size for BIRC assessed PFS

The audit size of the sample-based BIRC assessment will be 40% of all randomized patients. Based on the audit size calculation approach proposed by Dodd, et. al (2011), assuming investigator and BIRC assessments are similar and the estimated log of investigator-based HR is -0.40 (i.e., HR=0.67), the audit size of 40% will ensure that the upper bound of a one-sided 95% CI for BIRC-based log-hazard ratio has 86% probability of being below 0 (i.e. HR < 1) if the correlation between investigator assessment and BIRC assessment is 0.7 (the estimated correlation based on data from the BELLE-2 [CBKM120F2302] study in metastatic breast cancer).

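### The primary PFS data cut has two rules in the SAP, the projection tables follow the one that does not bind, and Protocol Table 10-1 still shows 90% PFS power instead of 95%

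*Protocol*

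**What the plan says.** Two SAPs are on file. This point concerns the one for the primary PFS analysis, written against protocol amendment 2. The SAP for the final study report has no event trigger.

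- **Timing, full rule.** Protocol 10.8 sets the final PFS analysis to be "done after approximately 125 events in the first line patients or approximately 364 events in both arms whichever comes later". SAP 3.16 agrees: "the final analysis will be done after approximately 125 events in the first line patients or approximately 364 events in both arms whichever comes later". The amendment 2 rationale says the first-line minimum was added so that enough information would come from first-line patients.
- **Timing, short rule.** SAP 2.2, which defines the data in the analysis, reads: "The primary PFS analysis will be carried out after approximately 364 events have been documented based on local investigator assessment". It does not mention first-line events.
- **Projections.** The first row of Protocol Table 10-1 and of SAP Table 3-9 puts the PFS analysis and first OS look at month 26, with 364 PFS events, 161 deaths (46%) and 14% OS power. The text repeats this in SAP 3.14.2 ("at which point a total of 161 deaths are expected"), SAP 3.8.2.1, the protocol summary, and Protocol 10.5.1 and 10.7.2. Protocol 10.8 and SAP 3.17 place the final OS analysis 30 months after the PFS analysis (56 − 26).
- **PFS power at 364 events.** Table 10-1, in the column "Power (%) against a hazard ratio of 0.67", gives 90. SAP Table 3-9, under "Cumulative Power (%) against a hazard ratio of 0.67", gives 95. Protocol 10.8 also states 95% and accounts for the change: "The increase in power from 90% to 95% while targeting the same hazard ratio and the number of events as in the original protocol", which it attributes mainly to dropping the futility interim.

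**The concern.** The cut-off rule fixes the date of the only PFS test and of the first OS look, so the SAP should contain one version of it. A team working from SAP 2.2 alone could cut the data at event 364. If the first-line condition is the later of the two, that cut would be short of first-line events, which is what the added rule was meant to prevent.

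The projections matter for the same reason. If the first-line condition binds, the OS look at the PFS analysis is later and carries more information than the tables show. Anyone judging how likely OS is to cross at that look, or how far apart the looks are, would be working from the wrong row. The 90 against 95 is a plain inconsistency in a stated power.

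**Working it through.** **Inputs.** From Protocol 10.8 and the Table 10-2 footnote: 660 patients, 2:1, 19-month uniform accrual; 40% first line and 60% second line; control median PFS 18 and 6.5 months; HR 0.67 (applied here to both lines); dropout hazard 0.0105. The unit is taken as per month, which gives 10.1% lost at month 26, matching the stated 10%. For OS: control median 30 months, HR 0.71, 10% lost by the final analysis at month 56, which requires a dropout hazard of about 0.00345 per month.

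**PFS power.** Power = Φ(√(d × 2/9) × |ln HR| − 1.96), with |ln 0.67| = 0.4005.

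- d = 364: √80.89 × 0.4005 − 1.96 = 1.64, so 95.0%. This reproduces the stated 95%.
- d = 295: 90.0%. So 90% does not belong with 364 events.
- d = 439: 97.7%.

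**Expected events.** For event hazard λ, dropout hazard η, h = λ + η and accrual R = 19, the probability of an observed event by month T (T ≥ R) is

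p(T) = (λ/h) × [1 − (e^(−h(T−R)) − e^(−hT)) / (hR)].

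| Group | n | λ per month | Events at T = 26.7 | Events at T = 35.7 |
|---|---|---|---|---|
| First line, control | 88 | 0.0385 | 38.3 | 49.3 |
| First line, ribociclib | 176 | 0.0258 | 56.8 | 75.7 |
| Second line, control | 132 | 0.1066 | 100.7 | 113.3 |
| Second line, ribociclib | 264 | 0.0714 | 168.2 | 200.4 |
| **First line, total** | 264 | | **95.1** | **125.0** |
| **All** | 660 | | **364.0** | **438.7** |

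Event 364 falls at month 26.7, against 26 stated, so the model reproduces the plan's timing. Only about 95 of those events are first line. The 125th comes about 9 months later.

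**Deaths.** The same formula with the OS inputs gives 167, 263 and 353 deaths at months 26, 39 and 56. The tables state 161, 263 and 351, and the Protocol 10.8 text states 353. At month 35.7 it gives 241 deaths, and 241/351 = 69% information.

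**First OS look.** Using the SAP 4.3.1 spending function with 351 final deaths:

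| Deaths at look 1 | Information | One-sided boundary p | Cumulative power at looks 1 / 2 / 3 |
|---|---|---|---|
| 161 (stated) | 46% | 0.0009 | 14 / 61 / 85% |
| 211 | 60% | 0.0038 | 37 / 60 / 85% |
| 241 | 69% | 0.0068 | 52 / 60 / 85% |

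The 161-death row reproduces the plan (14, 60, 85). With 241 deaths, the look comes 263 − 241 = 22 deaths and about 3 months before the next one. The final OS analysis is then 56 − 35.7 ≈ 20 months after the PFS analysis, not 30.

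**Sensitivity.**

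- No PFS dropout: event 364 at month 24.8 with 94 first-line events; the 125th at month 31.6 with 447 PFS events and 211 deaths; 24 months to final OS.
- Both PFS dropout values, with OS dropout from 0 to 0.0105: 197 to 251 deaths, 56% to 72% information, look-1 power 31% to 56%.
- First-line share 45%: 110 to 111 first-line events at event 364; the 125th comes with 396 to 401 PFS events.
- The two triggers coincide at a first-line share of about 49%.
- HR of 0.5 or 1.0 in both lines: about 96 first-line events at event 364.
- The 727 patients reported in amendment 2, with 12-month uniform accrual assumed and 40% first line: about 90 to 91 first-line events at event 364; the 125th at month 25.1 to 28.0 with 456 to 464 PFS events.

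**Precision in first line.** The 95% interval around HR 0.67 is 0.67 × exp(±1.96/√(d × 2/9)): 0.44 to 1.03 at 95 events and 0.46 to 0.97 at 125.

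**The case against.** SAP 2.2 can be read as incomplete rather than contradictory: 364 events remains a necessary condition under the later-of rule, and the full rule is in the same SAP. That is fair, but section 2.2 is where the cut is defined, and as written it would permit a cut that section 3.16 does not.

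The 660-patient, 19-month basis was already out of date when the rule was added, because amendment 2 records 727 patients enrolled in about 12 months. On that basis month 26 lies within the projected range, and amendment 3 dates the primary analysis to January 2018, about 31 months after a June 2015 start. So month 36 is not a forecast of what happened. This limits the claim to the plan's own assumptions, but it does not rescue the row: 364 events and 161 deaths remain too low on either basis.

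The death count and look-1 power depend on dropout and on the first-line share, and the documents do not report the actual share. At about 49% the discrepancy disappears. The OS model also gives 167 deaths at month 26 rather than 161. These are reasons to quote a range.

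Finally, nothing inferential turns on this. OS boundaries are recomputed from observed deaths (Protocol 10.7.2, SAP 4.3), first-line results carry no formal test, and the current protocol states that PFS and OS have both been met. All of that stands, and it is why the point is minor.

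**Conclusion.** The point holds as a minor documentation error with three parts. First, SAP 2.2 omits the first-line condition that Protocol 10.8 and SAP 3.16 require. Second, on the plan's assumptions that condition sets the date, so the first row of Table 10-1 and SAP Table 3-9 describes an analysis the rule would not produce. At a 40% first-line share the later-of rule gives about month 32 to 36, 439 to 447 PFS events and 211 to 241 deaths (197 to 251 across the OS dropout values tried), against month 26, 364 and 161. Third, the 90 in Table 10-1 should be 95 at 364 events.

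The first and third parts are visible from the text and need no modelling. The second rests on the stated 40% share, exponential times and a common HR in both lines. It weakens as the share rises and vanishes near 49%. PFS power rises to about 98%, cumulative OS power stays near 60% at 263 deaths and 85% at 351, and type I error is unaffected.

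**What to change.** 1. In SAP 2.2, state the full rule: about 125 PFS events in first-line patients (group A of the previous endocrine therapy factor, as SAP 3.16 defines it) or about 364 in total, whichever is later. Keep the 125-event requirement.
2. Recompute the first row of Protocol Table 10-1 and SAP Table 3-9 under that rule, and state the enrolment, dropout and first-line share used. On the 660-patient basis that the other rows already use: about month 36, 439 PFS events, 98% PFS power, 241 deaths, 69% and 52%. With no PFS dropout: about month 32, 447, 98%, 211, 60% and 37%. If 727 patients are used, redo the timing in all three rows. With 12-month accrual, 263 and 351 deaths then fall near months 32 and 45, so a 727-patient first row cannot sit beside months 39 and 56.
3. Align the sentences giving 161 deaths (protocol summary, Protocol 10.5.1 and 10.7.2, SAP 3.8.2.1 and 3.14.2) and the 30-month interval (Protocol 10.8, SAP 3.17), which becomes about 20 to 24 months on the 660-patient basis.
4. Wherever Table 10-1 still refers to 364 events, change 90 to 95.

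The cost is wording and one table row in each document. The test, the alpha, the number of looks and the event requirements do not change.
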